4.2 Intervention

Eligible patients with intermediate risk disease will be randomized to ADT with SBRT versus SBRT alone. The ADT patients will be treated with monthly degarelix injections. After three months (+/- 1 month) have elapsed, these patients as per routine would undergo fiducial marker placement followed by simulation and SBRT to follow. For this cohort ADT will continue until 6 months of Degarelix is administered. If a patient develops an allergic reaction to the Degarelix injection, he may be switched to Leuprolide acetate monthly injections in its place.

For patients treated with SBRT alone referral will be made for fiducial marker placement with simulation and SBRT to follow. Patients will then be followed at 6 month intervals with routine serum PSA and testosterone testing. All patients will undergo a post-SBRT standard 12 core prostate biopsy at 24-30 months after completion of SBRT to evaluate local tumor control status.

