8.0 PRETREATMENT EVALUATION

The following must be completed prior to randomization:

- MSKCC pathology review confirming cancer
- The following screening tests and assessments should be performed within 8 weeks prior to randomization to confirm eligibility:
 - Full medical history and physical exam, including DRE and performance status
 - MRI of the prostate and pelvis within 6 months of randomization. (CT of the pelvis with contrast may be performed if MRI is contraindicated)
 - Radionuclide bone scan if there is suspicion of bone metastases within 6 months of randomization.
 - Lab tests:
 - PSA
 - Baseline CBC, CMP (Na, K, Cl, CO₂, Ca, T. Protein, Albumen, Creatinine, Glucose, BUN, Alk Phos, ALT, AST, T. Bili), Conj. Bili,

- Testosterone level
- Questionnaires:
 - IPSS documenting score < 20
 - EPIC
 - SF-12

Once eligibility is confirmed, the patient should undergo randomization.

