10.2 Evaluation during Follow-Up

- Physical exam
- Performance status
- Clinical evaluation for late urinary, rectal toxicity and sexual dysfunction per standard CTCAE assessments and grading.
- PSA
- Serum Testosterone
- EPIC – 26
- SF-12
- IPSS
- Prostate biopsy, 24-30 months post SBRT

Table 1. Schedule of assessments

	Pre-Treatment	During Radiation Therapy	Follow up
	Within 8 weeks prior to study randomization	Within 2 week prior to the initiation of Degarelix ¹	
Informed consent	X		
Medical history	X		
Physical exam	X		X
Digital rectal exam	X		
Performance status	X		X
Histologic or pathologic confirmation of disease	X ²		
MRI prostate/pelvis within 6 months of randomization	X ³		
Bone scan within 6 months of randomization if determined necessary	X		
EPIC-26	X	X ⁴	X
SF-12	X	X ⁴	X
IPSS	X	X ⁴	X
PSA	X	X	X
CBC	X	X	
Comp	X	X	
Liver function tests	X	X	
Serum testosterone	X	X	X
Toxicity assessment			X
Degarelix		X ⁵	
Fiducial marker placement		X ⁶	
Radiation therapy		X'	
Biopsy			X ⁸

1. For patients randomized to the ADT + SBRT arm
2. Histologic or pathologic confirmation of disease can be done anytime prior to randomization.
3. CT of the pelvis with contrast may be performed if MRI is contraindicated.
4. To be completed during treatment, at the 3rd of 5th fraction of later
5. Degarelix will be given monthly (+/- 7 days), 3 months before and 3 months after radiation therapy.
6. Fiducial markers will be placed 3 days before simulation.
7. Radiation therapy will be given every other day.
8. Prostate post-treatment biopsy will be performed once at 24-30 months post SBRT.

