12.0 CRITERIA FOR THERAPEUTIC RESPONSE/OUTCOME ASSESSMENT

For the primary endpoint of this study, post-SBRT prostate biopsies will be performed to assess local tumor control for each of the treatment arms. While post-SBRT biopsies performed outside of MSKCC are permitted for the study, the central pathology review will be performed by the MSKCC pathology department. For the central pathology review, please send the study patients' post-SBRT prostate biopsy slides the address listed in the laboratory manual in appendix IV.

As has been well established criteria for the assessment of post-radiation biopsies (10), post-treatment biopsies will be categorized as negative if there is no evidence of adenocarcinoma, positive if there is evidence of adenocarcinoma (which could be assigned a Gleason score), or treatment effect ,where adenocarcinoma is noted displaying severe treatment effect precluding the assignment of a Gleason score. In our experience this latter classification is associated with a clinical behavior more consistent with a negative biopsy.

Biochemical recurrence will be determined according to the established Phoenix criteria of 2 ng/dL elevation of the PSA nadir level (nadir + 2 definition). Distant metastases will be defined as patients with imaging evidence or biopsy-proven metastatic disease in distant sites outside of the prostate most commonly in bone. Therefore the cumulative incidence of biochemical failure and distant failure will be computed by setting the starting time as the beginning date of the treatment until the event of interest, with death without the event of interest as the competing risk. Overall survival is defined from the beginning date of the treatment until death.

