13.0 CRITERIA FOR REMOVAL FROM STUDY

- Patient decides to withdraw from the study.
- Intercurrent illness that prevents treatment and/or follow-up imaging.
- Unacceptable adverse event that may be directly related to the protocol intervention.
- General or specific changes in the patient's condition that renders the patient unacceptable for further treatment, in the judgment of the investigator.
- Initiation of non-study therapy for prostate cancer.
- Does not meet inclusion/exclusion criteria.

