14.0 BIOSTATISTICS

The primary objective of this phase III trial is to compare 2-year biopsy positivity rate of intermediate risk prostate cancer patients treated with SBRT + short course ADT versus SBRT alone. The 2-year biopsy positivity rate will be calculated in each arm as a proportion of patients whose 2-year (from the end of SBRT) biopsy result is positive over patients who have 2-year biopsy results examined or whose 2-year biopsy results are regarded as positive (see the replacement rule below). We plan to analyze an evaluable sample of 200 patients, randomized in a 1:1 ratio to the two arms. This sample size has a power greater than 0.90 and type 1 error rate of 0.05 if the true 2-year biopsy positivity rates are 35% and 15% respectively, for the two arms using a two-sided, two-sample proportion test. This test will also be adjusted for the randomization stratification variables. Patients who died due to disease within 2 years from the end of SBRT will be regarded as having a positive biopsy. Patients who died not due to disease or are lost to follow-up within 2 years from the end of SBRT without any sign of progression will be replaced. To this end we will enroll an additional 10% patients upfront so the total sample size is 223. However, only the first 200 evaluable patients will be counted towards the primary endpoint. One interim analyses and one final analysis are planned (using equal spacing of looks) and the null hypothesis that the two arms have the same 2-year biopsy positivity rates will be rejected at these two looks if the p-values are <0.003 and <0.049, respectively, based on the Lan-DeMets alpha spending function approach. We expect that 100 patients will be enrolled each year, 50 from MSK and 50 between all regional sites. Therefore we anticipate to complete the enrollment in 2-3 years, plus an additional 2-year mandatory follow-up.

For the secondary objectives, the cumulative incidence rates of biochemical failure and distant failure will be evaluated by the competing risks method and Gray's test will be used to compare the two arms. Overall survival rates will be estimated by Kaplan-Meier method and compared by log-rank tests. QOL outcomes will be summarized and tabulated. Results from the two arms will be compared by Wilcoxon rank sum tests at time points when these surveys are conducted. All patients will be analyzed for the secondary objectives.

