15.2 Randomization

Patients will be randomized to receive ADT+SBRT, or SBRT alone. Immediately after consent is obtained, the RSA at MSKCC will register participants in the Clinical Trials Management System (CTMS). Once the participant's eligibility is established the registration will be finalized and the participants will be randomized using the Clinical Research Database (CRDB). Randomization will be accomplished by the method of random permuted block, and will be stratified by favorable vs unfavorable intermediate risk. After the treatment

arm is determined by randomization, the RSA will notify physicians at MSKCC of the treatment arm and participant ID via email within 24 hours of randomization.

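### The secondary failure and survival endpoints run from a treatment start date that follows randomisation, is ambiguous in the ADT arm, and is missing for patients who never start

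*Combined protocol and SAP*

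**What the plan says.** Section 12.0 obtains the cumulative incidence of biochemical failure and of distant failure by "setting the starting time as the beginning date of the treatment until the event of interest". For survival it says "Overall survival is defined from the beginning date of the treatment until death".

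Randomisation precedes any treatment. Section 8.0 reads "Once eligibility is confirmed, the patient should undergo randomization", and Section 15.2 has the same order.

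The arms then follow different paths. In the ADT arm degarelix comes first; Section 4.2 continues "After three months (+/- 1 month) have elapsed, these patients as per routine would undergo fiducial marker placement", with simulation and SBRT to follow. Table 1, footnote 5 (Section 10.2) says "Degarelix will be given monthly (+/- 7 days), 3 months before and 3 months after radiation therapy". Patients on SBRT alone go directly to fiducial placement, simulation and SBRT.

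Section 14.0 compares the failure endpoints by Gray's test and survival by the log-rank test, and adds "All patients will be analyzed for the secondary objectives". Among the reasons for removal in Section 13.0 is "Patient decides to withdraw from the study", with no limit to the time after treatment has begun.

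**The concern.** A randomised comparison is protected from the moment of randomisation. A later clock leaves out some follow-up, and here the amount left out can differ by arm. Three things are unresolved:

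- **Which date.** Nothing in Section 12.0 says whether treatment begins with degarelix or with SBRT in the ADT arm. Two competent analysts could build different datasets from this text.
- **Never-starters.** They have no start date and no rule covers them, yet all patients are to be analysed.
- **Either reading has a cost.** With an SBRT origin, an ADT patient who dies or withdraws during the degarelix lead has no valid time zero, so the arm is partly selected on reaching SBRT. With a first-treatment origin, the two clocks start at different points relative to SBRT.

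These endpoints make up the first secondary objective in Section 2.0. An origin left open can be chosen after outcomes are known.

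**Working it through.** **1. The plan's own figures.** No event count, hazard ratio or power is stated for these endpoints, so there is nothing to reproduce for them. The primary sizing does reproduce:

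- Power with 100 per arm, 35% against 15%: z = (0.20 × √100 − 1.96 × √(2 × 0.25 × 0.75)) / √(0.35 × 0.65 + 0.15 × 0.85) = (2 − 1.200)/0.596 = 1.34, so power is 0.91.
- Enrolment: 200/0.90 = 222.2, rounded up to 223.

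Neither depends on the secondary time origin. The primary endpoint has its own reference date, the end of SBRT.

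**2. The two readings side by side.**

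| Treatment start means | SBRT-alone clock | ADT clock | No valid time zero |
|---|---|---|---|
| First assigned treatment | first SBRT fraction | first degarelix | never-starters, either arm |
| SBRT | first SBRT fraction | first SBRT fraction | anyone who does not reach SBRT, including losses during the degarelix lead |

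**3. Distance between the two dates in the ADT arm.** Inputs: 3 ± 1 months of degarelix (Section 4.2), at least 3 days from fiducials to simulation (Section 9.1), and 14 ± 7 days from simulation to SBRT (Section 9.3).

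- Low: 2 + (3 + 7)/30.44 = 2.3 months
- Nominal: 3 + (3 + 14)/30.44 = 3.6 months
- High: 4 + (3 + 21)/30.44 = 4.8 months

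If the work-up falls inside the lead, as footnote 5 can be read, the gap is 2 to 4 months. Overall it is about 2 to 5 months. The 3 days is a minimum, so the high value is not a ceiling.

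**4. Patients affected.** The documents give no early loss rate. Assume death or withdrawal at q = 1-5% per year, 223/2 = 111.5 patients per arm, no delay from randomisation to work-up or first degarelix, work-up w = 10-24 days and lead m = 2-4 months. Expected losses before SBRT are 111.5 × (1 − exp(−q·w)) in controls and 111.5 × (1 − exp(−q·(w + m/12))) in the ADT arm, with w in years.

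- q = 1%: control 0.03-0.07, ADT 0.22-0.44
- q = 5%: control 0.15-0.37, ADT 1.08-2.20

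That is at most about two patients in the ADT arm under these assumptions. Each 1% of never-starters is 223 × 0.01 = 2.2 patients.

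**5. What a randomisation clock costs for biochemical failure.** Both arms have the work-up, so SBRT starts about m = 2-4 months later in the ADT arm. Assume the same constant hazard after SBRT in both arms, none before, and p = 10-15% failing by 3 years after SBRT (Section 3.2 reports under 15%). With h = −ln(1 − p)/3, the apparent difference at 3 years is p − [1 − exp(−h(3 − m/12))].

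| p | m = 2 | m = 3 | m = 4 |
|---|---|---|---|
| 10% | 0.53 | 0.79 | 1.06 |
| 15% | 0.77 | 1.16 | 1.55 |

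The values are percentage points in favour of ADT with no true effect. A work-up common to both arms changes them by less than 0.01. Under the same model an SBRT origin gives zero. A first-treatment origin gives the same values if the work-up lies inside the lead. If it follows the lead, the term becomes 3 − w − m/12 and the range is 0.62 to 1.86.

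**6. False-positive rate.** Log-rank simulations of this model (223 patients, 17-day work-up, no competing deaths, five follow-up patterns, 4,000 replicates per setting, Monte Carlo standard error about 0.004) gave 0.045-0.057 for an SBRT origin, 0.044-0.076 for randomisation and 0.048-0.080 for first treatment.

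**The case against.** The strongest reply is that the plan does mean SBRT. Section 9.0 labels SBRT the study treatment, the same in each arm. Section 9.3 uses the word treatment for starting SBRT. Table 1, footnote 4 defines being on treatment by fraction number. Under that reading, a common post-radiation clock is the cleaner one for biochemical failure, and moving to randomisation adds a shift that was not there.

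Much of this stands. A reader might infer that first degarelix is the natural meaning, but the documents do not show it. SBRT start is at least as plausible, although Section 9.0 also describes degarelix under the treatment plan and nothing ties its label to Section 12.0. A reader might also infer that a randomisation clock removes the timing shift. It does not: against a first-treatment origin it trims at most about 0.3 points (1.86 − 1.55), and against an SBRT origin it adds the 0.5 to 1.6 points.

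A further temptation is to say that never-starters will be dropped. No section excludes them, and Section 14.0 says the opposite. What is missing is a rule that makes its statement workable.

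It is also fair that censoring early withdrawals at last contact recovers little information, and that the nadir-based failure definition does not say how it applies to someone never treated. None of this supplies a time zero for deaths or withdrawals before SBRT.

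**Conclusion.** The point holds as a low-cost improvement to secondary endpoints. The origin follows randomisation, has two tenable meanings in the ADT arm about 2 to 5 months apart, and does not exist for never-starters, so the all-patients statement cannot be carried out as written. Randomisation is clearly the better origin for overall survival. For biochemical failure it is a trade-off that must be disclosed.

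The effect is probably small, and the documents do not give its size. The patient counts rest on an assumed 1-5% yearly loss and no delay after randomisation. The shift rests on equal constant hazards after SBRT and none before. A reader might infer material bias in the trial's conclusions; nothing here supports that. The primary biopsy endpoint, its power, its boundaries and the total of 223 are unaffected.

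**What to change.** In Sections 12.0 and 14.0, define time zero as the date of randomisation for overall survival, distant failure and biochemical failure, in all randomised patients by assigned arm. Event-free patients who never start are censored at last contact. Say how the nadir-based definition applies to them.

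State the downside next to the definition: because SBRT starts about 2 to 4 months later in the ADT arm, biochemical-failure incidence on this clock can look about 0.5 to 1.6 points lower there at 3 years with no true effect, under the assumptions above. Pre-specify a sensitivity analysis of biochemical failure timed from SBRT, labelled as not intention-to-treat, and name the date used (the end of SBRT would match the primary endpoint).

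The cost is a few sentences and one extra analysis. Randomisation is done in the clinical research database (Section 15.2), so its date should exist for every randomised patient. The sponsor should confirm that last-contact and survival data are kept for patients removed before treatment, because the plan does not say so. No change to sample size, visits or treatment follows.

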13.0 CRITERIA FOR REMOVAL FROM STUDY

- Patient decides to withdraw from the study.
- Intercurrent illness that prevents treatment and/or follow-up imaging.
- Unacceptable adverse event that may be directly related to the protocol intervention.
- General or specific changes in the patient's condition that renders the patient unacceptable for further treatment, in the judgment of the investigator.
- Initiation of non-study therapy for prostate cancer.
- Does not meet inclusion/exclusion criteria.

14.0 BIOSTATISTICS

The primary objective of this phase III trial is to compare 2-year biopsy positivity rate of intermediate risk prostate cancer patients treated with SBRT + short course ADT versus SBRT alone. The 2-year biopsy positivity rate will be calculated in each arm as a proportion of patients whose 2-year (from the end of SBRT) biopsy result is positive over patients who have 2-year biopsy results examined or whose 2-year biopsy results are regarded as positive (see the replacement rule below). We plan to analyze an evaluable sample of 200 patients, randomized in a 1:1 ratio to the two arms. This sample size has a power greater than 0.90 and type 1 error rate of 0.05 if the true 2-year biopsy positivity rates are 35% and 15% respectively, for the two arms using a two-sided, two-sample proportion test. This test will also be adjusted for the randomization stratification variables. Patients who died due to disease within 2 years from the end of SBRT will be regarded as having a positive biopsy. Patients who died not due to disease or are lost to follow-up within 2 years from the end of SBRT without any sign of progression will be replaced. To this end we will enroll an additional 10% patients upfront so the total sample size is 223. However, only the first 200 evaluable patients will be counted towards the primary endpoint. One interim analyses and one final analysis are planned (using equal spacing of looks) and the null hypothesis that the two arms have the same 2-year biopsy positivity rates will be rejected at these two looks if the p-values are <0.003 and <0.049, respectively, based on the Lan-DeMets alpha spending function approach. We expect that 100 patients will be enrolled each year, 50 from MSK and 50 between all regional sites. Therefore we anticipate to complete the enrollment in 2-3 years, plus an additional 2-year mandatory follow-up.

For the secondary objectives, the cumulative incidence rates of biochemical failure and distant failure will be evaluated by the competing risks method and Gray's test will be used to compare the two arms. Overall survival rates will be estimated by Kaplan-Meier method and compared by log-rank tests. QOL outcomes will be summarized and tabulated. Results from the two arms will be compared by Wilcoxon rank sum tests at time points when these surveys are conducted. All patients will be analyzed for the secondary objectives.

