Retrospective data from Memorial Sloan-Kettering Cancer Center have demonstrated that improved distant metastases-free survival and prostate cancer mortality survival outcomes are observed with the addition of short course ADT to high-dose (≥ 81 Gy) conventionally fractionated radiotherapy among patients with intermediate risk disease (3). Between 1992 and 2007, 1024 patients with NCCN intermediate risk prostate cancer were treated at Memorial Sloan Kettering Cancer Center and its regional facilities with definitive external beam radiation with doses of ≥ 81 Gy. Unfavorable intermediate risk factors were defined as primary Gleason score (GS) of 4, percentage of positive biopsy cores (PPBC) $\geq 50\%$, and more than one intermediate risk factors (IRF). Unfavorable intermediate risk patients had at least one of these factors, whereas favorable intermediate risk patients had none, with a median follow-up was 6 years. 51% of patients received short-course androgen deprivation therapy (ADT). In that study we noted that ADT was associated with an improvement in all outcomes in our multivariate models. Patients with unfavorable intermediate risk disease had inferior rates of PSA-RFS (HR = 2.37, 95% CI: 1.68-3.36, P <0.0001), DM (HR=4.34, 95% CI: 1.95-9.67, P=0.0003), and PCSM (HR=7.39, 95% CI: 1.75-31.31, P = 0.007) compared to those with favorable intermediate risk disease. Patients with multiple unfavorable risk factors had particularly poor prognosis, with 8 year rates of PSA-RFS, DM, and PCSM of 60%, 23%, and 12%, respectively. Benefits of using ADT were most noted among patients with intermediate risk features with unfavorable characteristics. In a prior publication we also noted improved post-treatment biopsy outcomes among patients who were treated with external beam radiotherapy (EBRT) with the addition of a short-course of ADT compared to external radiotherapy alone short course NAAD had a significant impact on the posttreatment biopsy outcome. Of patients who did not receive ADT 86 of 206 (42%) had a positive biopsy compared to 21 of 133 (16%) who received ADT (p <0.0001). Zelefsky MJ, Reuter VE, Fuks

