4.0 OVERVIEW OF STUDY DESIGN/INTERVENTION

4.1 Design

For this proposed Phase III study, intermediate risk patients will be randomized to received 6 months of ADT which would be given 3 months prior to planned SBRT to the prostate and 3 months during/following SBRT. ADT will be administered via Degarelix monthly injections. SBRT will be delivered with a prescription dose of 8 Gy x 5 prescribed to the planning target volume. Inter-fraction motion targeting and target position correction will be utilized as is routine in our department during the treatment SBRT.

The primary end-point of this study is the proportion of patients who have positive 2-year post-treatment prostate biopsies. Based on our previous published experience, we expect that the 2-year rate of a positive biopsy using ADT with ultra-hypofractionated SBRT for intermediate risk features would be 15% compared to 35% for those patients treated with SBRT alone. We anticipate we would require powering the study with 100 patients in each arm. Randomization will be stratified by favorable-intermediate and unfavorable-intermediate risk status (unfavorable-intermediate risk will be defined as patients having Gleason 4+3, >50% positive biopsy cores or 2 intermediate risk factors combined such as Gleason 7 and PSA > 10 ng/ml).

The primary endpoint is the 2-year biopsy which is generally scheduled at the end of the second year. However, we have provided some flexibility as to prevent prospective and retrospective deviations. Therefore, we have chosen to allow the primary endpoint biopsy to occur between 24-30 months which we believe is reasonable based on our clinical experience.

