6.0 CRITERIA FOR SUBJECT ELIGIBILITY

6.1 Subject Inclusion Criteria

- Biopsy proven intermediate risk prostate cancer, which includes patients with any one of the following variables:
 - Gleason 7 disease
 - PSA 10-20 ng/ml
 - Clinical T2b-T2c disease

Note: Patients who only have radiographic evidence of T3 disease (i.e. extracapsular extension, or seminal vesical invasion radiographically) will not be excluded.

- Serum testosterone \geq 240 ng/dL determined within 2 months prior to enrollment
- At least 4 weeks must have elapsed from major surgery
- KPS \geq 80%
- Prostate size as determined on MRI to be $<$ 90 cc. Prostate size can be determined on CT scan if MRI is not available.
- 18 years of age or older
- IPSS \leq 20
- Patient must be available for follow-up. After 2 years of follow-up following post-treatment biopsy, telephone-based follow-up will be acceptable
- Laboratory test findings within 8 weeks of randomization:
 - Adequate hepatic function with serum bilirubin \leq 1.5 times the upper institutional limits of normal (ULN), ALT and AST \leq 2.5 x ULN. Patients with a history of Gilbert's syndrome may be enrolled if the total bilirubin is $<$ 3 mg/dL with a predominance of indirect bilirubin
 - Adequate renal function with serum creatinine \leq 1.5 x ULN
 - Adequate hematologic function with absolute neutrophil counts \geq 1,500 cell/mm³ and platelets \geq 100,000 cells/mm³ and hemoglobin value \geq 9 g/dL (Note: patients whose anemia has been corrected to a hemoglobin value \geq 9 g/dL with blood transfusions are allowed)

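### The primary test adjusts only for a two-level risk stratum; adding two prespecified continuous baseline covariates could bring a small gain in precision

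*Combined protocol and SAP*

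**What the plan says.** Section 14.0 sets the design: "We plan to analyze an evaluable sample of 200 patients, randomized in a 1:1 ratio to the two arms". The comparison is made "using a two-sided, two-sample proportion test", and power is claimed "if the true 2-year biopsy positivity rates are 35% and 15% respectively". The claim itself reads "This sample size has a power greater than 0.90 and type 1 error rate of 0.05". On covariates there is one sentence: "This test will also be adjusted for the randomization stratification variables". Neither the method of adjustment nor the effect measure is named. There are two looks, at nominal levels 0.003 and 0.049.

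Sections 4.1 and 15.2 show that the stratification is a single factor with two levels. Section 4.1 gives the rule: "unfavorable-intermediate risk will be defined as patients having Gleason 4+3, >50% positive biopsy cores or 2 intermediate risk factors combined", with Gleason 7 plus PSA above 10 ng/ml as the example of a combination.

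Section 8.0 requires PSA and a prostate MRI (CT if MRI is contraindicated) before randomization. Section 16.0 lists PSA and biopsy results among the data to be collected. Radiographic stage is not listed there, although Section 6.1 does not exclude this group: "Patients who only have radiographic evidence of T3 disease".

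**The concern.** A two-level stratum pools unlike patients. A man becomes unfavorable through any one of three routes, and the adjustment treats one route the same as all three. Section 3.1 says of the centre's own series: "Patients with multiple unfavorable risk factors had particularly poor prognosis", with 8-year PSA relapse-free survival of 60%, distant metastasis of 23% and prostate cancer mortality of 12%. If a similar gradient applies to biopsy positivity, the stratum captures only part of it.

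PSA must be measured before randomization, and percent positive cores must be known to assign the stratum. About 50 positive biopsies are expected. If these variables predict the outcome within strata, chance imbalance in them adds noise to the comparison that a prespecified model could remove without enrolling another patient. At stake is a modest amount of precision in a trial with little spare power, not the validity of the test.

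**Working it through.** **Inputs from Section 14.0.** 100 evaluable per arm; 35% v 15%; two-sided 0.05 overall; looks at 0.003 and 0.049.

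**Reproducing the stated power.**
- Null standard error: √(2 × 0.25 × 0.75 / 100) = 0.0612.
- Alternative standard error: √((0.35 × 0.65 + 0.15 × 0.85) / 100) = 0.0596.
- Power = Φ[(0.20 − z × 0.0612) / 0.0596], which gives 0.910 at 0.05 (z = 1.960) and 0.909 at 0.049.
- Exact enumeration of the pooled z-test gives 0.914 and 0.913.
- 90% power needs 97 per arm, so the claim of more than 0.90 holds with no covariates at all.
- Levels of 0.003 and 0.049 at equal spacing give an overall type I error of 0.04998.

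**Size of the possible gain, by variance scaling.** Let R² be the share of outcome variance explained beyond the stratum. The documents give no value, so a range of 0 to 0.20 is assumed. The variance is multiplied by (1 − R²). Power at 0.049 is then Φ[0.20 / (0.0596 × √(1 − R²)) − z × 0.0612 / 0.0596], and effective n per arm is 100 / (1 − R²).

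| Assumed extra R² | Power at 0.049 | Effective n per arm | 95% CI half-width (points) |
|---|---|---|---|
| 0 | 0.909 | 100 | 11.7 |
| 0.02 | 0.914 | 102 | 11.6 |
| 0.05 | 0.922 | 105 | 11.4 |
| 0.10 | 0.935 | 111 | 11.1 |
| 0.20 | 0.958 | 125 | 10.4 |

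If the true rates were 35% v 20%, power would be 0.660 at R² = 0, 0.683 at 0.05 and 0.706 at 0.10.

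This scaling ignores the cost of estimating the covariate effects. In a simulation of a linear model with robust standard errors (4,000 trials per setting, Monte Carlo standard error up to about 0.005), stratum only was compared with stratum plus four covariates. Power went from 0.912 to 0.904 when the covariates were not prognostic. It went from 0.919 to 0.930 when total R² was about 0.08 to 0.12.

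**Simulated power of the short logistic score test at 0.049** (assumed prognostic strength):

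| Added prognosis beyond the stratum | Mantel-Haenszel | Score test | Gain |
|---|---|---|---|
| None | 0.916 | 0.917 | 0.001 |
| Moderate | 0.932 | 0.938 | 0.006 |
| Strong | 0.930 | 0.949 | 0.019 |

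**Type I error.** Expected positives are 100 × 0.35 + 100 × 0.15 = 50 at the final analysis. At an equally spaced interim there are about 100 patients and 25 positives. A six-term model (arm, stratum, log PSA, primary Gleason 4, continuous cores, radiographic T3) has 25 / 6, or about 4, positives per term at that look. The four-term model has 25 / 4, or about 6. Simulated null rejection rates with assumed covariate distributions were:

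| Test | Interim, nominal 0.003 | Final, nominal 0.049 |
|---|---|---|
| Six-term standardised risk difference, uncorrected standard error | 0.006–0.0075 | 0.055–0.059 |
| Short logistic score test | 0.003–0.0035 | 0.047–0.054 |
| Stratum-adjusted Mantel-Haenszel | about 0.002–0.0033 | 0.048–0.052 |

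The six-term model also failed to fit in 1–2% of interim trials.

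**The case against.** The strongest reply is that nothing is broken. Adjusting for the stratification factor is valid and prespecified, the stated power reproduces without covariates, and chance imbalance is already allowed for in the type I error. All of that stands.

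The evidence for within-stratum prognosis is also indirect. Section 3.1 reports PSA relapse, metastasis and mortality after conventionally fractionated radiotherapy. No section links PSA, Gleason pattern, cores or T3 to biopsy positivity. This stands too, and it is why only a range of gains can be given.

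A third objection is that a richer model can damage the interim look. It is correct for a six-term standardised risk difference with an uncorrected standard error. It does not hold for the short score test, which stayed close to nominal at both looks.

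A reader might infer that PSA, Gleason pattern and percent positive cores are not used at all. Section 4.1 rules this out, because the stratum is built from them. A reader might also infer that a man with seminal vesicle invasion on imaging and one other factor is always classed as favorable. He is not if that factor is Gleason 4+3, or if more than 50% of his cores are positive. Radiographic T3 is outside the stratum rule, but Section 16.0 does not list it as a data item and Section 8.0 allows CT in place of MRI. It cannot be assumed to be available on a uniform basis.

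**Conclusion.** The point holds as an optional efficiency improvement. The primary test uses PSA, Gleason pattern and percent positive cores only in dichotomised form, and within-stratum information available at baseline goes unused. With the short score test, power at 0.049 rises by about 0 to 2 points at 35% v 15%, with essentially no gain if the covariates add nothing beyond the stratum. These figures rest on assumed covariate distributions and prognostic strength.

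It would be tempting to conclude that the trial is underpowered, or that it demonstrably gives up precision. The documents support neither. The stated power is met, and a loss of precision could be shown only with an association between these variables and biopsy positivity, which the documents do not report.

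**What to change.** In Section 14.0, before any outcome data are seen:

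- Specify the primary test as the score test for arm from a logistic model with arm, stratum, log baseline PSA and percent positive cores (continuous), at the existing levels of 0.003 and 0.049.
- Report the standardised risk difference from that model with a small-sample-corrected standard error. This also settles the adjustment method and effect measure, which are now unnamed.
- Keep the stratum-adjusted Mantel-Haenszel test as the sensitivity analysis.
- Do not base the test on a six-term standardised risk difference with an uncorrected standard error.
- Leave radiographic T3 out unless it is captured as a data item.

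The cost is a few sentences, a little programming and a short covariate list locked in advance. Percent positive cores must be recorded as a value and not only as above or below 50%. No extra patients or visits are needed.
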